Serious adverse events—Study One

There will be no individual case adverse event reporting for Study One, which is a retrospective study using data linkage.

Serious adverse events—Study Two

This study is following women for four weeks following vaccination. Should there be any cases of stillbirth, fetal death, spontaneous abortion, elective abortion or other significant pregnancy outcomes during the period of active data collection, that we become aware of, these will be reported within 24 hours.

Reporting will occur on pregnancy outcomes, fetal outcomes and neonatal status at the end of the study for the Study One participants.

There will be no causality assessment performed as the study staff will not be able to do this based on telephone interviews. However causality process is undertaken via the established NZ CARM process.

The investigators and study team will be clearly informed and reminded of the importance of this timely reporting of any SAE to CARM.

Serious adverse events—Study Three

This study is following women for 12 months following vaccination. Should there be any cases of stillbirth, fetal death, spontaneous abortion, elective abortion or other pregnancy outcomes during the period of active data collection these will be reported within 24 hours of notification.

There will be no causality assessment performed as the study nurses will not be able to do this based on telephone interviews.

The investigators and study nurses will be clearly informed and reminded of the importance of this timely reporting of any SAE to CARM.

Data sharing with OCEANS database

We intend to enable data sharing for Study Two and Three with the OCEANS database. We await information from GSK on the database requirements. Data sharing of de-identified information will enable rapid transfer of information on both serious and **non-serious adverse events**. The data sharing will be covered in the Ethical approval and in the patient informed consent.

The data to GSK will be provided in MS Excel format. All variables collected in Study 2 and 3 will be provided in this file.

Other adverse event reporting:

Adverse events not meeting criteria for an SAE that are subject to clinician verification/review will be reported to CARM according to local requirements at the discretion of the clinician/investigator.

The Investigators shall report all clinical safety data defined below. In addition, the investigators will report any other clinical safety data arising during the study at such times as GSK may require.

Definition—SAE

A SAE is any untoward medical occurrence that, at any dose:

- a) Results in death
- b) Is life-threatening

NOTE: The term 'life-threatening' in the definition of 'serious' refers to an event in which the subject was at risk of death at the time of the event. It does not refer to an event, which hypothetically might have caused death, if it were more severe.

c) Requires hospitalisation or prolongation of existing hospitalisation

NOTE: In general, hospitalisation signifies that the subject has been detained (usually involving at least an overnight stay) at the hospital or emergency ward for observation and/or treatment that would not have been appropriate in the physician's office or out-patient setting. Complications that occur during hospitalisation are AEs. If a complication prolongs hospitalisation or fulfils any other serious criteria, the event is serious. When in doubt as to whether "hospitalisation" occurred or was necessary, the AE should be considered serious.

Hospitalisation for elective treatment of a pre-existing condition that did not worsen from baseline is not considered an AE.

d) Results in disability/incapacity

NOTE: The term disability means a substantial disruption of a person's ability to conduct normal life functions. This definition is not intended to include experiences of relatively minor medical significance such as uncomplicated headache, nausea, vomiting, diarrhoea, influenza, and accidental trauma (e.g., sprained ankle) which may interfere or prevent everyday life functions but do not constitute a substantial disruption.

e) Is a congenital anomaly/birth defect

f) Medical or scientific judgment should be exercised in deciding whether reporting is appropriate in other situations, such as important medical events that may not be immediately life-threatening or result in death or hospitalisation but may jeopardise the subject or may require medical or surgical intervention to prevent one of the other outcomes listed in the above definition. These should also be considered serious. Examples of such events are invasive or malignant cancers, intensive treatment in an emergency room or at home for allergic bronchospasm, blood dyscrasias or convulsions that do not result in hospitalisation, or development of drug dependency or drug abuse.

AE definitions

An AE is any untoward medical occurrence in a patient or clinical investigation subject or consumer, temporally associated with the use of a product, whether or not considered related to the product.

Examples of an AE include:

Exacerbation of a chronic or intermittent pre-existing condition including either an increase in frequency and/or intensity of the condition

New conditions detected or diagnosed after investigational product administration even though it may have been present prior to the start of the study

Signs, symptoms, or the clinical sequelae of a suspected interaction

Signs, symptoms, or the clinical sequelae of a suspected overdose

Examples of an AE do not include a/an:

Medical or surgical procedure (e.g., endoscopy, appendectomy); the condition that leads to the procedure is an AE

Situations where an untoward medical occurrence did not occur (social and/or convenience admission to a hospital)

Anticipated day-to-day fluctuations of pre-existing disease(s) or condition(s) present or detected at the start of the study that do not worsen

The disease/disorder being studied, or expected progression, signs, or symptoms of the disease/disorder being studied, unless more severe than expected for the subject's condition

All as per Brighton Collaboration where these definitions are available.

Definitions for local reactions and fever	
Local Reactions	Systemic Events

Level one diagnostic certainty is: Any description of morphological or physiological change at or near the injection site that is described or identified by a health care provider
 
Level two diagnostic certainty is: Any description of morphological or physiological change at or near the injection site that is described or identified by another person
 
Categories for event classification
 
Level 1: as specified in the case definition for a local reaction
 
Level 2: as specified in the case definition for local reaction
 
Insufficient evidence for a local reaction Not a case of a local reaction
 
Interval for onset of local reaction or first observation
 
>0-24 h 25-48 h 49-72h 73h – 7 days >7 days
 
Include numbers of subjects with local reactions newly present at each specified time as %.
 
Diameter of the local reaction
 
>0.0 - <1.0 cm ≥1.0 – 2.5 cm
	
Fever
 
Endogenous elevation of at least one measured body temperature of ≥38°C
 
Time intervals
 
0 – 24hr Day 1 0 – 24hr Day 2 Day 3-7...
 
Increments
 
<38°C 38.0-38.4°C 38.5-38.9°C Etc.... >41°C

≥2.5 – 5.0 cm ≥5.0 - <10.0 cm ≥10.0 - <15.0 cm ≥15.0 - <20.0cm ≥20.0 - <30.0 cm ≥30.0 cm
 
Pain scale to include measure of functionality
 
0 = No pain 1 = Mild, still able to move arm normally 2 = Moderate, hurts to move arm normally or to touch 3 = Severe, unable to move arm
	
--	--

Ethical considerations

Ethical approval for this study will be obtained from the NZ Ministry of Health and Disability Ethics Committee. These guidelines are based on statements from NZ and international guidelines, including the World Medical Association Declaration of Helsinki: Ethical principles for medical research involving human subjects (WMA 2008) and the Council for International Organizations of Medical Sciences' International Guidelines for Ethical Review of Epidemiological Studies (CIOMS 1991).

Details about the National Ethics Advisory Committee and the Ethical Guidelines for Observational Studies can be accessed <http://neac.health.govt.nz/streamlined-ethical-guidelines-health-and-disability-research>

Whilst we are not undertaking any clinical work (there is no intervention, only observation), we will be observing the standards required by the national ethics committee and GCP standards, in which our team are familiar.

We intend acknowledging participating practices for their nursing time taken in identifying participants and assisting in recruitment and acknowledging patient participants for their time taken to respond to interviews. Reimbursement will be in the form of retail vouchers: the amount of which the practice receives will be determined by the time and effort provided to recruit our study participants. Patient participants will each receive a \$40 supermarket or petrol voucher. This is line with acceptable NZ practice for reimbursement but dependent on approval from the ethics committee.

Protocol registration

A Universal Trial Number (UTN) has been allocated by the World Health Organization specifically for Studies One and Two (U1111-1148-0718). These studies were subsequently registered with the Australian New Zealand Clinical Trials Registry (ANZCTR) and allocated the ACTRN: ACTRN12613001045707.

Dissemination of results

Results will be disseminated via the following mechanisms:

Report and presentation to the funder

[figure not shown]
Report and presentation to the NZ MoH and Pharmac

Presentations considered for ESPID or other appropriate infectious disease and vaccine and vaccination conferences

Publication/s in international pertinent journal such as *Vaccine* or *Paediatrics*

Itemised Study Budget

See detailed budget in separate spreadsheet.

Pertussis Budget Summary 2013-2015	Total Cost (NZD)	Percentage of Total Cost	Comments
Staff Costs	\$600,800	69%	Academics, Project Manager, Research Nurse and Data Analyst
Christchurch Study	\$197,700	23%	[name], Research Nurse and Participant Payments
Koha/Participant Payment	\$24,000	3%	Payment to participants and participating GP practices
Telecommunications and Consumables	\$47,800	5%	Telephones, Office Costs, Data Extraction
TOTAL COST	\$870,300	100%	

Curriculum vitae

New Zealand MSI Curriculum Vitae Template

PART 1

1a. Personal details				
Full name	Title	First name	Second name(s)	Family name
	[name]	[name]
Present position	Senior Lecturer, Dept. General Practice and Primary Health Care Director of Research, Immunisation Advisory Centre			
Organisation/Employer	University of Auckland/ UniServices			
Contact Address	[name]			
	[name]			
	Auckland		Post code	
Work [contact]	[contact]	
Email	[contact]			
Personal website (if applicable)	http://immune.org.nz			

1b. Academic qualifications

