All participants in this study will be de-identified.

Outcomes

Hospitalisation outcomes of interest will include the following conditions.

Mother	ICD-10-CM
Still birth, preterm birth pregnancy complications	P95 Stillbirth ⁹ O60 Preterm labour Z37 Outcome of delivery 
 • Single stillbirth • Twins, one liveborn and one stillborn • Twins, both stillborn • Other multiple births, all stillborn O00-O99.9 Pregnancy, childbirth and the puerperium
Infant	
Certain conditions originating in the perinatal period	Newborn affected by maternal factors and by complications of pregnancy, labour, and delivery P00-P96
Early neonatal death, SIDS	Ill-defined and unknown causes of mortality R95-R99.9
Congenital anomalies (CVS, CNS, other)	Congenital malformations, deformations and chromosomal abnormalities Q00-Q99.9
Infectious Diseases (pertussis, , etc.)	Certain infectious and parasitic diseases A00-B99
Meningitis	Meningitis due to other and unspecified causes G03 
 •arachnoiditis NOS •leptomeningitis NOS •meningitis NOS •pachymeningitis NOS
Encephalitis	Encephalitis, myelitis and encephalomyelitis G04 
 •acute ascending myelitis •meningoencephalitis •meningomyelitis
Lower respiratory (bronchiolitis, asthma, pneumonia, acute unspecified LRTI, bronchiectasis, Acute bronchitis, lung abscesses/pyothorax	Diseases of the respiratory system J00-J99
Neurological	Diseases of the nervous system G00-G99

⁹ Information about stillbirths is recorded in the Mortality Collection. The Mortality Collection includes extra information about fetal and infant deaths, such as gestation and birth weight. The ICD codes we propose are: P95 Fetal death of unspecified cause Z37 Outcome of delivery, Z37.1Single stillbirth, Z37.3 Twins, one live born one stillborn, Z37.4 Twins, both stillborn, Z37.7 Other multiple births, all stillborn

Pregnancy duration will be classified using the gestational age field from the National Maternity Collection data set. This field gives the duration of pregnancy in number of completed weeks. Preterm will be defined as birth before 37 weeks gestation. Normal term will be defined as birth between 37 and 41 weeks gestation. Post-term will be defined as birth after 41 weeks gestation.

The following codes are available so we can get banded weeks of gestation.

1518 Duration of pregnancy

Code	Number	
O09.0	<5	Completed weeks
O09.1	5-13	Completed weeks

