6-week check	Written questionnaire (Appendix 6) administered by telephone to GP to determine pregnancy outcome and medically attended adverse events in mother since last contact.	Written questionnaire (Appendix 6) administered by telephone to GP practice to capture birth history, weight and head circumference, any congenital abnormalities, neonatal death (<29 days) Details of 6-week check and confirm receipt of 6-week vaccination. Document any prior GP or hospital visits.	If an unsolicited adverse event is noted during these calls, it will follow the same safety reporting procedures as other AEs in the study.
3–6 month check		Weight, head circumference, vaccination status, and standardised clinical examination by Plunket Nurse as recorded in Well Child book (Appendix 6). ³	
1-year follow-up		Final contact with mother about pertussis exposure and/or symptoms. Vaccination status – if not completed infant vaccinations by 6 months.	

1 Three attempts will be made to contact mother by telephone within 1 week of notification of receipt of Tdap. If an e-mail address is available this will also be used if telephone contact is unsuccessful.

2 Written questionnaire will be sent to mother before 4 weeks have elapsed since receipt of vaccine. Telephone contact will be made at 4 weeks of receipt of vaccine and two further times if the completed questionnaire has not been received within 1 week.

3 Mothers will be encouraged to attend Plunket for check ups during the first 6 months. If there is no available recorded weight and head circumference between 3-6 months of age this will be done by a member of the study team. The mother will be contacted three times via email or phone to get this information.

4 Three attempts will be made by phone or email to contact the mother each month

*Persistent cough lasting for >10 days and/or post-tussive vomiting

** Close contact defined as being in the same room as the person for > 1 hour or 5 minutes of face to face contact with a person with proven pertussis who was symptomatic.

Data management/Data confidentiality

Data will be managed and protected according to the requirements of the Ethical approval. An Access database will be developed to receive the data reported on the survey forms (Study Two and Three).

Data set fields will be identified

Code tables will be created

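### Study One defines early neonatal death by ill-defined and unknown cause codes alone (R95-R99.9), so early deaths with a known cause would not be counted as deaths

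*Protocol*

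**What the plan says.** The Outcomes section of Study One opens its table with "Hospitalisation outcomes of interest will include the following conditions". Among the infant rows, "Early neonatal death, SIDS" carries the single entry "Ill-defined and unknown causes of mortality R95-R99.9". The row states no age at death, date of death, discharge status or vital status.

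The causes from which a newborn might die have rows of their own. Examples are "Newborn affected by maternal factors and by complications of pregnancy, labour, and delivery P00-P96", "Congenital malformations, deformations and chromosomal abnormalities Q00-Q99.9" and "Certain infectious and parasitic diseases A00-B99"; there are also respiratory (J00-J99) and neurological (G00-G99) rows. None of them has a death element.

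A mortality source is mentioned once, in footnote 9: "The Mortality Collection includes extra information about fetal and infant deaths, such as gestation and birth weight". That footnote is attached to stillbirth and proposes only P95 and Z37 codes. The five databases listed for Study One under Study procedures are the National Minimum Dataset, the National Immunisation Register, the ESR notifications, the HealthPAC claims and the National Maternity Collection. The Mortality Collection is not among them.

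**The concern.** The label names an event fixed by age at death, whatever the cause. The codes select a group of causes, at whatever age. The two overlap only for early deaths that were left unexplained.

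The outcome carries weight. The protocol's first aim concerns health outcomes in infants of vaccinated mothers, and the clinical hypothesis covers infant outcomes to one year. Study One, with about 325,000 births, is the only component large enough to say anything about rare deaths. Study Three does record neonatal death by age, but in about 300 women: with no events among 300, the upper 95% bound is still about 3/300 = 1%. A reassuring odds ratio on the Study One row would naturally be taken as a statement about early neonatal mortality, which it would not be.

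**Working it through.** No figure is stated for this outcome (no rate, event count or power), so there is nothing to reproduce. The check is to follow individual infants through the rules as written.

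**Rules used**

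1. Outcome row and codes: Study One, Outcomes table (R95-R99.9; no age limit).
2. Infant follow-up: first year of life (Study One, Study participants).
3. Source of hospital outcomes: National Minimum Dataset (Study One, Study participants and Study procedures).
4. Counting: one count per person per hospitalisation, on the primary diagnosis (Statistical analysis, Study One, Analysis).

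**Four hypothetical infants**

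| Infant | Early neonatal death in fact? | Row that captures it | Counted as early neonatal death? |
|---|---|---|---|
| A: dies on day 3, cause coded in P00-P96 | Yes | P00-P96 | No |
| B: admitted with the same code, survives | No | P00-P96 | No |
| C: dies on day 3, cause unexplained | Yes | R95-R99.9 | Yes |
| D: dies at five months, cause unexplained | No | R95-R99.9 | In the same row as C |

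A and B cannot be told apart in the outcome data, because the P00-P96 row has no death indicator. The same holds if A's cause lies in Q00-Q99.9, A00-B99, J00-J99 or G00-G99. C and D share a row. They could be separated only by a breakdown by age, for which no window is given.

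**Size**

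Let s be the share of early neonatal deaths coded R95-R99.9. The share not counted as deaths is 1 − s. The protocol gives no deaths by cause, so s is unknown and the documents do not bound 1 − s more narrowly than 0 to 100%.

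**Whether another section supplies the definition**

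- Footnote 9 concerns stillbirth, and its source is not on the list of data to be obtained.
- The one fatal outcome with its own analysis is stillbirth (the survival analysis).
- The Study One analysis text says serious adverse events will be described as clinical cases, while the safety section says Study One has no individual case reporting. Even on the first reading, narratives would need the deaths to be identified first and would not compare vaccinated with unvaccinated.
- Study Three's age-based record (under 29 days) applies only to Study Three.

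No section gives Study One an all-cause or age-based definition of infant death.

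**The case against.** Several points against the concern have force.

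- **The events are not lost.** A reader might infer that deaths with a known cause vanish from Study One. They do not: a death in hospital can still appear under its diagnosis. What is lost is its identification as a death.
- **The loss cannot be sized.** A reader might also infer that most early neonatal deaths are missed. A figure of 80–95% would follow if only 5–20% were coded ill-defined or unknown, but nothing in the protocol supports that share.
- **SIDS belongs in the row.** Its label includes SIDS, so counting later unexplained deaths there is intended. Infant outcomes are also to be described by age, which could partly separate early from later events. That eases the mixing of C and D above, but does nothing for A.
- **There is no contradiction with Study Three.** The two definitions differ, and this might be read as an inconsistency. Study Three is a separate descriptive study, pooling is promised only for maternal data from Studies Two and Three, and its term is neonatal death, not early neonatal death. Nothing requires a match.
- **The list is open, and an analysis plan not seen here may refine codes.** The table's opening words allow further outcomes. They do not alter the codes given for this one: the protocol did not leave the definition to be settled later.

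These points limit how much can be claimed. None supplies the missing definition.

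**Conclusion.** The concern holds as a mismatch between label and definition. Followed as written, the plan gives a wrong count for a named infant safety outcome: early deaths with a known cause are left out of it and pooled with survivors elsewhere. A null result on the row would be uninformative about early neonatal mortality. This conclusion rests only on the protocol's own labels and code ranges, and on taking early neonatal death in its ordinary sense as a death defined by age. Its numerical size is unknown, and the point should be made without a percentage.

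**What to change.** Three changes to the protocol:

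1. **Outcome.** Define early neonatal death as death from any cause within a stated age window, with age computed as date of death minus date of birth. State whether early neonatal death, neonatal death (for example the under-29-day limit recorded in Study Three) or both are meant. Alignment with Study Three is an option, not a requirement.
2. **Source.** Add the Mortality Collection, which footnote 9 says covers infant deaths, to the Study One databases under Study procedures. The new source alone is not enough: if the R95-R99.9 filter stayed on the row, known-cause deaths would still be excluded.
3. **Separate outcome.** Report SIDS and ill-defined causes (R95-R99) on their own over the first year of life.

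The cost is more than an edit to the table, since a further national dataset must be obtained and linked. NHI linkage is already planned for Study One and every birth is assigned an NHI number, so no new linkage method is needed.

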Intensive safety monitoring (Study Three) *Canterbury District Health Board (DHB), [name] (PI)*

To describe adverse events in women who were administered Tdap under the DHB programme between 30–36 weeks of gestation

To describe outcomes of babies whose mothers were vaccinated with Tdap in the Canterbury region during week 30 to 36 of pregnancy (including birth history, weight and head circumference and any congenital abnormalities)

Clinical hypothesis

The rates and patterns of adverse events following administration of Tdap during pregnancy (including the rates and patterns of any adverse pregnancy outcome, and the outcomes in infants up to one year of age), are similar to those where no vaccination during pregnancy occurred.

Background

New Zealand (NZ) is currently experiencing a significant increase in pertussis. The number of notified cases has risen dramatically from July 2011 and remained high throughout 2012. Increases in pertussis notifications have been seen previously and occur over a four- to five-year cycle in NZ. The underlying reasons for such a cycle are unknown.

Notification data and associated rates by age indicate that the under-one-year-olds are the most vulnerable with a cumulative notification rate in 2012 of 606 per 100,000 or 378 cases, 167 being hospitalised. This is the highest cumulative notification rate of any age group in 2012. There were 40 notifications of infants under six weeks old, 36 of which were hospitalised.

In 2012 (up to 23 November) 287 hospitalisations were reported. Of these, 167 (58.2%) were infants under one year old. Two deaths were reported, one in a three-year-old unimmunised child with underlying health conditions, and one in an infant aged less than six weeks with a history of preterm birth. All infants hospitalised with pertussis infection younger than six weeks of age have not received their first pertussis immunisation. Data in NZ shows about 20% of infant cases are infected by their mothers.¹

The most recent data for the two surveillance weeks (24 November–7 December 2012) showed 248 new cases of pertussis (113 and 135 cases, respectively) notified, including 111 confirmed cases, 92 probable cases, 14 suspect cases, and 31 cases still under investigation. Twenty-nine (11.7%) of the notified cases were aged less than one year. Fourteen cases were hospitalised.

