Infants remain susceptible to pertussis until they have responded immunologically to the primary series of infant pertussis immunisations. As immunity (measured as serum antibody) derived from both natural infection and vaccination wanes over several years, most mothers pass little protective antibody via transplacental transfer to their unborn infant. However when present, pertussis IgG has been demonstrated to be effectively transferred from mother to infant.²

Recently the US Advisory Committee on Immunization Practices (ACIP) recommended that acellular pertussis vaccine (Tdap) be given to any person likely to be in contact with young infants under the age of 12 months, including pregnant women.³ Administering the vaccine to pregnant women is advised because it not only offers protection to the mother from pertussis but as a result of the maternal booster response provides for maternal antibody to be passed to the infant, which may be protective for the first few weeks of life.

There are no theoretical safety concerns with administering subunit vaccines to pregnant women and some vaccines, such as tetanus, are used widely in this group. ACIP acknowledged that the safety of Tdap immunisation during pregnancy has not been systematically studied, with the only data available coming from small studies, post-marketing surveillance, and the US Vaccine Adverse Event Reporting System (VAERS).⁴ They concluded that

¹ Walls R. Pertussis (whooping cough) epidemiology in Waikato, New Zealand: 2000–2009. *NZ Med J* 2011;124(1332).

² Leuridan E, Hens N, Peeters N, de Witte L, Van der Meeren O, Van Damme P. Effect of a prepregnancy pertussis booster dose on maternal antibody titers in young infants. *Pediatric Infectious Disease Journal* 2011 Jul;30(7):608-10.

³ United States Centers for Disease Control and Prevention. Updated recommendations from the Advisory Committee on Immunization Practices (ACIP). *MMWR* 2011; 60(41): 2011

⁴ US Advisory Committee on Immunization Practices. Summary Report. Atlanta, Georgia: ACIP; February 23-24, 2011. Available from <http://www.cdc.gov/vaccines/recs/acip/downloads/min-feb11.pdf> Accessed 23 April 2012.

available data from these studies did not suggest any elevated frequency or unusual patterns of adverse events in pregnant women who received Tdap and that the few serious adverse events reported were unlikely to have been caused by the vaccine.

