The large retrospective component to this study adds significant power to the overall study: It is a cost effective method of data collection and enables more effective assessment of seasonality. It will also provide data on a range of pregnancy and birth outcomes which are not readily available from a prospective study design (e.g., Apgar scores).

⁵ New Zealand Ministry of Health. Current advice on the public health management of pertussis. Wellington: MoH; 5 April 2012. Available at http://www.nzdoctor.co.nz/media/1682109/pertussis_letter_moh_5_apr_2012.pdf

⁶ New Zealand Ministry of Health. Chapter 15: Influenza. In Immunisation Handbook 2011. Wellington: MoH; 2011. Available at

http://www.google.co.nz/url?sa=t&rct=j&q=ministry%20health%20influenza%20vaccine%20pregnant%20women%20funded%20&source=web&cd=7&ved=0CGYQFjAG&url=http%3A%2F%2Fwww.health.govt.nz%2Fsystem%2Ffiles%2Fdocuments%2Fpublications%2F15influenza.pdf&ei=8SiWT8iDH4_m8QQgnNGMCG&usq=AFQjCNFUuAYDXQKxJFmqXKd4PBfzm1i2A

⁷ Canterbury District Health Board. Media release from Canterbury DHB: Free whooping cough vaccine extended to pregnant women. Christchurch: CDHB; April 19, 2012.

⁸ Study Three is largely funded by Canterbury DHB, but is being conducted as part on the three-component study covered in this protocol. Study Three runs as per Study Two, except the former study will follow women and their infants for a period of one year after the birth of the infant while the follow up for the latter study is to four weeks post vaccination.

Study design

Study One: Retrospective analysis of safety outcomes for pregnant women vaccinated with TdaP vaccine and their infants.

Study population

All women delivering in NZ for the study period 2009–2013 and their infants will form the overall study population. Study One will identify all pregnancies and all exposures (except the very few who privately purchased the vaccine).

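### The Study One infant infection outcome (A00-B99) has pertussis, the vaccine's target disease, inside it, so a block odds ratio would mix an intended benefit with the safety question

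*Protocol*

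**What the plan says.** Protocol, Study One, is titled "Retrospective analysis of safety outcomes for pregnant women vaccinated with TdaP vaccine and their infants". In its Outcomes table, the infant row labelled "Infectious Diseases (pertussis, , etc" is given the code range "Certain infectious and parasitic diseases A00-B99". No section takes pertussis out of that range or defines a non-pertussis infection outcome.

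Three other places bear on the row:

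- **Background:** vaccination in pregnancy "provides for maternal antibody to be passed to the infant, which may be protective for the first few weeks of life". For infants under one year the same section reports "a cumulative notification rate in 2012 of 606 per 100,000 or 378 cases, 167 being hospitalised".
- **Clinical hypothesis:** rates and patterns of adverse events, including infant outcomes to one year, "are similar to those where no vaccination during pregnancy occurred".
- **Statistical analysis, Study One:** logistic regression gives odds ratios for exposed against unexposed. The added explanatory variables are age, ethnicity, deprivation and season of admission. Calendar year is not among them.

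Under Study participants and Study procedures, pertussis notifications are also obtained from ESR and linked to vaccine status by NHI number.

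**The concern.** If the vaccine works as the Background hopes, pertussis should be less frequent in exposed infants. Similarity is then not the expected result for an outcome that contains pertussis, and one odds ratio has to carry two effects with different meanings. A value near 1 could be no effect, or a rise in other infections offset by fewer pertussis admissions.

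Timing adds a second problem. According to Study population, regional funding began in 2012 and national funding in October 2012, and earlier private purchase cannot be identified. The Background dates the rise in notifications from July 2011. Identified exposure therefore falls within the epidemic, while many unexposed births come before it. Without adjustment for calendar time, pertussis inside the block could raise the exposed group's rate for reasons unrelated to the vaccine.

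**Working it through.** **Protocol figures reproduced.** Study One size: 5 x 65,000 = 325,000 births, as stated. Infant share of pertussis hospitalisations: 167/287 = 58.2%, as stated. No power, significance level or detectable effect is given for Study One.

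**Inputs from the Protocol (Background).**

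- Infants implied by the notification rate: 378 / 606 x 100,000 = 62,376.
- Pertussis admission risk under one year: 167 / 62,376 = 0.268%. The 167 is the count to 23 November 2012, so the full-year figure is not lower.
- Pertussis admission risk under six weeks: 36 / 62,376 = 0.058%.

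**Assumptions, not in the Protocol.** Total A00-B99 admission risk T of 2-5%, and protection VE against pertussis admission of 50-90%.

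**Hidden increase.** With preventable pertussis risk p, the block risk ratio (RR) is exactly 1 when the relative increase in the rest of the block is VE x p / (T - p).

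| Protection covers | T = 5%, VE 50% | T = 5%, VE 90% | T = 2%, VE 50% | T = 2%, VE 90% |
|---|---|---|---|---|
| First six weeks (p = 0.058%) | 0.6% | 1.1% | 1.5% | 2.7% |
| Whole first year, 2012 rate (p = 0.268%) | 2.8% | 5.1% | 7.7% | 13.9% |

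The first row leaves later pertussis in the rest of the block. Removing all under-one pertussis from the denominator moves its top value to 0.9 x 0.0577 / (2 - 0.268) = 3.0%.

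**Sensitivity.** At one third of the 2012 rate (0.089%) and T = 3%, with whole-year protection, the hidden increase is 1.5-2.8%. If A00-B99 admissions are rare (T = 1%), whole-year protection at the 2012 rate could hide 18-33%.

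**What is lost in detection.** Take 97,500 exposed (the Protocol's 30%) and 227,500 unexposed, an assumed two-sided 5% level, T = 3%, VE = 70% over the whole year at the 2012 rate, and a true RR of 1.10 for other infections.

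- Non-pertussis risk is 3 - 0.268 = 2.732%, which becomes 3.006%. Pertussis becomes 0.268 x 0.3 = 0.080%.
- Block RR = 3.086 / 3 = 1.03, power 26%. With pertussis excluded, RR = 1.10, power 99%.
- At one third of the pertussis rate the block RR is 1.08, with power 93% against 99%.
- At T = 8% and the 2012 rate, power for RR 1.10 is 100% either way. For RR 1.05 it falls from 96% to 48%.
- If protection stops at six weeks (T = 3%, 2012 rate), pertussis becomes 0.268 - 0.7 x 0.058 = 0.227%, and the block RR is 3.233 / 3 = 1.08.

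**Direction.** Suppose exposed infants face the 2012 pertussis rate, unexposed infants average one third of it, and non-pertussis risk is 2.732% in both groups, so there is no true harm. The unexposed block risk is 2.732 + 0.089 = 2.822% before rounding its parts.

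- Whole-year protection of 50%: (2.732 + 0.134) / 2.822 = 1.02.
- Whole-year protection of 90%: (2.732 + 0.027) / 2.822 = 0.98.
- Six-week protection of 50%: (2.732 + 0.239) / 2.822 = 1.05.

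The one-third figure is illustrative. The sign depends on how epidemic timing and protection balance.

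**The case against.** The strongest reply is that the table is a list of code ranges for extraction and does not define composite endpoints. Its rows overlap: G03 and G04 lie inside G00-G99, and O60 inside O00-O99.9, a range that would count childbirth itself. The analysis text speaks of specific adverse events and specific diagnoses, and no section prescribes a single odds ratio for A00-B99. Pertussis is measured separately through ESR, and the objectives include examining differences in infant hospital outcomes, so pertussis is a legitimate outcome. Grouping within a range could also be settled in a SAP, which was not available here.

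Much of this stands. A reader might infer that the Protocol commits to a block-level test, or that a ratio below 1 would be credited to safety. The text states neither. What remains is that this table is the only definition of the infant infection outcome and it expressly puts pertussis inside. The separate notifications allow pertussis to be counted alone but do not take it out of A00-B99.

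The reply is also right on size. The Background claims protection that "which may be protective for the first few weeks of life". Applying 50-90% protection to all 167 under-one admissions goes beyond that claim, and the under-six-weeks count of 36 is the closer match.

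**Conclusion.** The point holds as a correctable flaw in an outcome definition. If A00-B99 is analysed as written, its odds ratio mixes the vaccine's target disease with the infection safety question. At 2-5% total risk and 50-90% protection, it could hide a relative increase of about 0.6-2.7% if protection ends at six weeks. The upper case, about 3-14%, needs protection through the whole first year at the epidemic-year rate. The total risk and the protection are both assumptions, so the size cannot be fixed from the Protocol.

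Two stronger readings are not supported. One is that the outcome cannot answer the safety question at all: larger harms would still show unless A00-B99 admissions are rare. The other is that the distortion always masks harm: exposure is concentrated in 2012-2013 and calendar year is not a listed covariate, so a false increase is also possible. The change is advisable because it is cheap and deals with the pertussis contribution in either direction.

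**What to change.** In the Study One infant outcome table, replace the single infection row with two:

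1. Pertussis, from hospital codes and the linked ESR notifications, reported as an effectiveness outcome.
2. A00-B99 excluding pertussis, as the infant infection safety outcome.

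State that the similarity hypothesis applies to the second row only. The separate pertussis result still has to be read with the epidemic timing in mind.

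The cost is one more row. The table already lists G03 and G04 beside G00-G99, so the format allows it, and the data are already to be obtained and linked. The safety outcome loses some events: at the 2012 rate, 0.268/5 to 0.268/2, or about 5-13% under the 2-5% assumption, and fewer outside the epidemic.
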